Fortunately, there are interventions that reduce risk for bloodstream infection in home TPN. In a retrospective study, chlorhexidine gluconate transparent antimicrobial dressing reduced CRBSI from eight cases to zero case in 12 months.¹⁵ Another research study found that patients with parenteral nutrition who are managed by a dedicated nutrition support team are less likely to develop CRBSI at 24 months than a variety of physicians (1.3% vs 26.2%).¹ More importantly, patient engagement and education program has been proven feasible and potentially effective. An oncology unit in Denmark developed an education program for 42 out of 82 randomized patients with tunneled central vein catheters. 88% of the 42 patients completed the training, and the 42 patients had 50% less CRBSI in a five-month period.¹⁶ A group in MD Anderson Cancer Center designed an in-person and video education program for central catheter care. After 1 year, 95% of the participating patients caring for the catheters at home, and 97% of them reported confidence and satisfaction in catheter care.¹⁷

We developed an education video addressing the aseptic techniques to safely handle central catheters at home for TPN use. It will be hosted in a mobile app with a secure link. Our primary aim is to assess the effect of the video training supplementation prior to discharge on the rate of CRBSI over a 12-month period of time. Our secondary aims are

to assess the patient's comfort level when handling catheters for patients newly initiated home TPN.

Hypothesis

We hypothesize that 1) the video will improve rates of CRBSI compared to a control group receiving written catheter instructions; 2) the video will improve patients' comfort level with handling central catheters; 3) patients will find the video easy to use.

Participants

Inpatient adult patients who are discharged home for the first time on home TPN will be approached for consent and inclusion in this prospective study design.

Study duration

24 months

Methodology

Inclusion Criteria

1. Patient will be discharged to start TPN at home.
2. Age ≥ 18 yrs.
3. Ability to understand and sign written consent form.
4. English-speaking patients.
5. Patients who are willing to self-administer TPN at home.

Exclusion Criteria

1. Patients without consent
2. Patients who have been on home TPN prior to the index admission at any time in the past
3. Non-English-speaking patients
4. Patients who will not self-administer TPN.

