If a subject fails to respond to these electronic questionnaires, the IRB-approved study staff will approach he/she during a standard GI Nutrition follow-up clinic visit to obtain answers for the questionnaire via a secure link on a tablet device.

The follow-up period will not exceed one year beyond the inclusion date. At the end of one year, the IRB-approved study staff will gather clinical information from the electronic medical record to determine if each subject has had a CRBSI event. Per CDC, CRBSI is defined as a laboratory confirmed infection where a Central Venous Catheter (CVC) is in place for over 2 calendar days prior to a positive culture and is also in place the day of or day prior to culture. And not deemed as a result from contamination by the primary hospital team at the time of the treatment.

The subjects will undergo weekly laboratory tests (complete blood count, electrolytes, liver function, and kidney function) as part of their routine standard of care to ensure the TPN formula is up to date and meets subjects' nutritional and metabolic needs. If a subject seeks care outside of UChicago, subject's UChicago care team members will obtain permission to have the health information released to UChicago, as part of the subject's standard of care. If patient wishes to transfer care of their TPN and CVC permanently to another institution, then their participation in this study will be terminated.

Additionally, subjects will be followed-up weekly via phone by their care team at UChicago as part of subjects' routine standard of care to ensure safe use of CVC and TPN infusions.

Study Schema

Assessment/Procedure	Visit 1	Visit 2	Visit 3	Visit 4
Informed consent	X			
Data collection: Demography and medical history	X			
Randomization	X			

Watch video/ follow written instructions	X	X	X	
Complete questionnaire	X	X	X	
Review medical, surgical, and hospitalization records for CRBI evaluation				X

Location

Patients will be consented at the University of Chicago's Center for Care and Discovery and Mitchell Hospital. All obtained data will be stored in a password protected computer or a locked drawer in the research office in M-421.

Potential risks and benefits

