There is a minor risk of loss of confidentiality with participation in this study since subject identifiers will be collected. However, all study data will be recorded in a database where names and medical record numbers will be removed and replaced with a study I.D. Only the study staff will have access to the key which links the study code to the subject's identity.

Patients may receive no direct benefit from participation in this study, but it is anticipated they will benefit from improve catheter self-care techniques, and an improved physicians' understanding of catheter associated bloodstream infections.

Special Precautions

No specimens will be collected during this study. Standard precautions will be provided during all patient encounters and clinical care.

Special precautions will be taken by research staff to ensure confidentiality. All data review will be performed electronically on a password-protected computer in a locked and limited access area.

Data will be coded in case the study team needs to go back and re-check data or look into abnormalities. Subjects are assigned a unique study code in place of their name and MRN. Only the study staff will be able to link data with subjects' identifiable information. Upon termination of the study, the coding link will be destroyed, leaving only completely de-identified data.

Experimental controls and use of placebos

N/A

Number of experimental subjects

One hundred (100) subjects will be included in the study.

Data Analysis

The rate of CRBSI will be determined. Risk factors for the CRBSI will be assessed in univariable and multivariable analysis based on pre-defined clinical and subjective risk factors.

Statistical justification

The rationale for the number of subjects is as follows. With 30% rate of bloodstream infection, and a 70% power and 95% confidence interval, the total sample size required would be 93 patients in order to see a reduction in the rate of bloodstream infection. Suppose a 10% rate for loss to follow-up, the total subjects will be 100 patients.

At the end of the study, the rate of CRBSI will be calculated and compared between the TPN video group and the control group using an unpaired Student's T test. The frequency of TPN video use will be reported as quantitative data based on discrete values. The comfort level of CVC handling will be aggregated, and the mean value will be compared between the video group and the control group using an unpaired Student's T test.

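### The printed CRBSI definition excludes only contamination, so read literally it counts bloodstream infections with another documented source; the likely cost is some power, not bias

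*Combined protocol and SAP*

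**What the plan says.** The event is defined in the Methodology section of the protocol. It is "a laboratory confirmed infection where a Central Venous Catheter (CVC) is in place for over 2 calendar days prior to a positive culture", and the catheter must also be in place on the day of the culture or the day before. The only exclusion follows: the event is "not deemed as a result from contamination by the primary hospital team at the time of the treatment". The definition is attributed to CDC, but no CDC document, version or further criterion is cited there or in the reference list.

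At one year, study staff use the electronic record to "determine if each subject has had a CRBSI event". The Study Schema lists this at Visit 4 as "Review medical, surgical, and hospitalization records for CRBI evaluation". No section says how the source of an infection is to be judged, or that the person judging is unaware of the study arm.

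The Background describes the intervention as an "education video addressing the aseptic techniques to safely handle central catheters at home for TPN use". Under Statistical justification, "the rate of CRBSI will be calculated and compared between the TPN video group and the control group" by an unpaired t test. The sample size is set "With 30% rate of bloodstream infection, and a 70% power and 95% confidence interval", and the stated total before losses is 93.

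**The concern.** The video teaches catheter handling, so it can be expected to prevent infections that enter through the catheter. A patient with a catheter in place whose bloodstream infection is traced in the records to another site meets every printed condition. Contamination does not cover that case, because the infection is real. Patients in this trial may have such sites: Appendix 1 asks about an ostomy, a fistula and a G tube, but nothing links the answers to event classification.

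Two things are at stake. Events that the video is not designed to prevent would enter both arms, widen the standard error of the difference and make the relative effect look smaller. And two staff members reading the same chart could classify it differently, one by the printed words and the other by the usual sense of catheter-related. The plan aims for only 70% power, so there is little precision to give away.

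**Working it through.** **Inputs from the protocol.** Rate 30% (read as the control rate), power 70%, 95% confidence, 93 patients before losses, 100 enrolled, 10% lost (Statistical justification). 100 × 0.9 = 90, or 45 per arm. The Background reports 50% less CRBSI over five months in a randomized patient-education study in an oncology unit.

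**Assumptions.** Equal arms; two-sided 5%; each patient scored 0 or 1; the 30% includes other-source events; the video affects only catheter-source events; no patient has both kinds. The other-source share of control events, f, is not in the documents and is varied.

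**Formulas.** SE = √[(p1(1−p1) + p2(1−p2))/n]; power = Φ(|p1−p2|/SE − 1.96).

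**The plan's own figure.** The video-arm rate is not stated, so 93 cannot be reproduced from the printed inputs alone. Solving for it with 46.5 per arm gives about 10%. As a check, N = 2 × (1.960 + 0.524)² × (0.21 + 0.09)/0.20² = 92.6, or 93. This solution is not unique: a one-sided version with a 12% video rate gives 92, and a one-sided version with continuity correction and 10% gives 94.

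**Effect of the definition.** Let r be the relative reduction in catheter-source events.
- As printed: 0.30 vs 0.30f + 0.30(1−r)(1−f).
- With other-source events excluded: 0.30(1−f) vs 0.30(1−r)(1−f).

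Worked case, r = 1/2, f = 0.20, n = 45:
- As printed: 0.30 vs 0.18. SE = √[(0.2100 + 0.1476)/45] = 0.0891. Power = Φ(0.12/0.0891 − 1.96) = 27%. Risk ratio 0.60.
- With the exclusion: 0.24 vs 0.12. SE = √[(0.1824 + 0.1056)/45] = 0.0800. Power = Φ(0.12/0.0800 − 1.96) = 32%. Risk ratio 0.50.
- The difference is 12 points either way. The variance ratio is 0.3576/0.2880 = 1.24.
- Expected events: 13.5 + 8.1 = 21.6 as printed; 10.8 + 5.4 = 16.2 with the exclusion.

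| Share f | Halving: printed vs excluded | Two-thirds reduction: printed vs excluded |
|---|---|---|
| 0 | 41% both | 69% both |
| 5% | 37% vs 39% | 63% vs 66% |
| 10% | 34% vs 37% | 58% vs 63% |
| 20% | 27% vs 32% | 46% vs 56% |
| one third | 20% vs 27% | 33% vs 47% |

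Only the gap within a cell is due to the definition. The rest of the fall down a column occurs either way, because fewer events are preventable.

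**Two assumptions varied.** If the two sources are independent, so that a patient can have both, then at halving and f = 0.20 the excluded version compares 25.5% with 12.8%, with power 34% against 27% as printed. If instead the 30% is purely catheter-source and an independent other-source risk q comes on top, power under halving with 93 analysed falls from 42% to 38% (q = 3%), 35% (q = 5%) or 30% (q = 10%).

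**When the exclusion stops paying.** Suppose a fraction m of true catheter-source events is wrongly excluded, equally in both arms. Under halving, power equals that of the printed definition at m = 8% (f = 10%), 16% (f = 20%) and 29% (f = one third).

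**The case against.** The strongest reply is that the endpoint's name already restricts the source. The Background spells CRBSI out as catheter-related, staff are told to look for a CRBSI event, and the definition is credited to CDC. On that view a reviewer would never count an infection traced elsewhere. This stands in part: it cannot be said that such infections will be counted. But the text goes on to print what reads as a complete definition, with one exclusion, and the narrower criterion appears nowhere.

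A second reply is that the size is unknown and perhaps small. That stands. The share is not given, under halving a 5% share costs less than 2 points, and power is already only 41% at share zero. The missing effect size and the small sample limit this trial more than the definition does.

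A third reply is that a source judgement could bring in bias that the printed rule does not have. That also stands. For illustration, take a 20% share, no true effect, and 20% of true catheter events wrongly excluded in the video arm only: 24% vs 24% × 0.8 = 19.2%, a spurious benefit of 4.8 points.

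A reader might also infer that the missing word blood lets a urine or wound culture count. The endpoint is named a bloodstream infection throughout, so that is a matter of tidying the wording.

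**Conclusion.** The point holds as a gap in the printed definition with a modest, uncertain cost. Under the halving reported in the Background, excluding other-source events would recover about 3 to 7 points of power at shares of 10% to one third, less than 2 points at 5%, and nothing at zero. The cost reaches 5 to 15 points only with the two-thirds reduction, which is back-solved from the sample size and is not stated in the plan. All these figures rest on an assumed share and on 45 analysed per arm.

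A reader might infer that the definition biases the trial for or against the video. The documents do not support that for the planned rate difference: randomization should spread other-source infections about equally, and the difference is unchanged when no patient has both kinds of infection. If some do, it shrinks slightly (12.0 against 12.8 points in the independent case above). What does move is the risk ratio, from 0.50 to 0.60 at a 20% share under halving, and the reported CRBSI rate, which is too high in both arms. The change is worth making because it is cheap and settles an ambiguity in the primary endpoint.

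**What to change.** In the rule for the Visit 4 record review, count a positive blood culture as CRBSI only if the records do not document another site of infection with the same organism around the time of that culture. Before review starts, write down the time window and the evidence required, including whether a matching culture from the other site is needed. Have the existing study staff apply the rule to record extracts that do not show the study arm. Report the definition as now printed as a sensitivity analysis.

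The cost is a short addition to the definition, the preparation of extracts without the arm, and one extra analysis; no new visit or data source is needed. The downside is fewer counted events (about 16 instead of 22 in the worked case) and a judgement on source. The break-even fractions above show how much equal error would cancel the gain. Unequal error between arms would bias the comparison, so masking to arm is part of the change. The sensitivity analysis shows how much the judgement matters, but it does not restore events wrongly excluded.

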Appendix 1: Central Catheter Teaching and Self-Care Initial Questionnaire

Name: _____ Subject ID: _____
 Date: _____ Email: _____

- 1) What type of central venous catheter do you have?
 PICC line Tunneled catheter (Hickman)
- 2) How many lumens (or "ports") on your catheter? _____
- 3) What are the cycle hours of your PN (parenteral nutrition)? _____ hours
- 4) Do you use any other IV medications through the catheter (excluding heparin lock, etc for catheter maintenance only)? Yes No

What IV medications?

	Yes	No
Do you currently have an ostomy?		
Do you currently have a fistula anywhere in your body?		
Do you currently have a G tube?		
Have you ever worked with IVs in a home or employment setting?		

- 5) How comfortable do you feel about taking care of your central venous catheter?
 - Very uncomfortable
 - Somewhat uncomfortable
 - Neutral
 - Somewhat comfortable
 - Very comfortable

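### The CRBSI definition does not tie the infection to the home PN catheter, so infections of other central lines can count as primary events

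*Combined protocol and SAP*

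**What the plan says.** The Background describes an "education video addressing the aseptic techniques to safely handle central catheters at home for TPN use" and gives the primary aim as the "effect of the video training supplementation prior to discharge on the rate of CRBSI over a 12-month period of time".

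The Methodology contains the only event rule. A CRBSI is a "laboratory confirmed infection where a Central Venous Catheter (CVC) is in place for over 2 calendar days prior to a positive culture", with a catheter also in place on the day of the culture or the day before. The one printed exclusion is contamination: "And not deemed as a result from contamination by the primary hospital team at the time of the treatment".

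On the observation window, the Methodology says "The follow-up period will not exceed one year beyond the inclusion date". Participation also ends on permanent transfer of TPN and catheter care elsewhere, and a patient may withdraw. No text ends event counting when home PN stops or the home catheter is removed. Staff find events at Visit 4 by reviewing medical, surgical and hospitalization records at the end of the year.

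**The concern.** The intervention acts on how patients handle their own catheter at home. The event rule uses the indefinite article, so any central line present for long enough satisfies it. Two kinds of infection would meet the rule although home self-care has no bearing on that line: infection of a line placed and handled in hospital at a later admission, and infection of a line placed after home PN ended. Excluding contamination removes neither.

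Such events should be about equally frequent in both arms. They would shrink the observed relative effect, add variance, and make the reported rate something other than a home PN catheter infection rate. The risk-factor analysis in Data Analysis would inherit the same mixture. The trial is planned at only 70% power, so it has little margin. An abstractor who meets such a case in the records also has no printed rule for excluding it.

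**Working it through.** **Inputs from the documents** (Statistical justification): 30% event rate, 70% power, 95% confidence, 93 patients before loss to follow-up, 100 in total with 10% loss.

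**Assumptions:** 1:1 allocation; two-sided 5% test; 45 evaluable per arm (100 × 0.90 / 2). The video-arm rate is not stated. The share of events from other lines is not given, so it is varied: 1, 3, 5 or 8 of the 30 control percentage points.

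**Step 1: the plan's 93.** It cannot be derived from the printed inputs alone, because no effect size is given. With 30% versus 10% and unpooled variance:

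n per arm = (1.96 + 0.524)² × (0.30×0.70 + 0.10×0.90) / 0.20² = 46.3, or 92.6 in total.

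This matches 93, so 30% versus 10% (a two-thirds reduction) is used as one scenario. A halving, 30% versus 15%, gives 186 with the same formula and each arm rounded up, so it does not reproduce 93. It is kept as a second scenario because the Background cites a patient-education trial with 50% less CRBSI.

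**Step 2: power formula** (pooled variance under the null):

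power = Φ{ [ |p₁−p₂| − 1.96·√(2p̄(1−p̄)/n) ] / √([p₁(1−p₁)+p₂(1−p₂)]/n) }, n = 45.

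Undiluted, 30% vs 10%: (0.20 − 1.96×0.0843)/0.0816 = 0.425, so power is 66.5%.

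**Step 3: other-line events.** Let x be the part of the 30% that comes from other lines and r the rate ratio for home-catheter events. As printed, the arms are 0.30 and x + (0.30−x)r. Restricted, they are 0.30−x and (0.30−x)r. Example with x = 0.03, r = 1/3:

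- As printed, 0.30 vs 0.12: (0.18 − 1.96×0.0859)/0.0837 = 0.140, power 55.6%; observed relative reduction 60% instead of 67%.
- Restricted, 0.27 vs 0.09: (0.18 − 1.96×0.0810)/0.0787 = 0.270, power 60.6%.

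The difference between arms is 0.18 either way. The gain comes only from lower variance.

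| Other-line points of 30 | Two-thirds effect: as printed | restricted | gain | Halving: as printed | restricted | gain |
|---|---|---|---|---|---|---|
| 1 | 62.9% | 64.6% | 1.7 | 37.3% | 38.3% | 1.0 |
| 3 | 55.6% | 60.6% | 5.1 | 32.6% | 35.5% | 2.9 |
| 5 | 48.3% | 56.6% | 8.2 | 28.3% | 32.8% | 4.4 |
| 8 | 38.1% | 50.3% | 12.2 | 22.6% | 28.8% | 6.2 |

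Gains are taken before rounding.

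**Step 4: the other parameterisation.** If 30% is already the home-catheter rate and 3 points of other-line events are added to both arms (33% vs 13%), power falls from 66.5% to 61.9%. Restriction then recovers all of that, about 5 points.

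**The case against.** The strongest answer is that context supplies what the article omits. Every participant goes home on self-administered TPN. Appendix 1 asks "What type of central venous catheter do you have" and offers one type per subject. Elsewhere the Methodology uses CVC for the TPN line, as in "If patient wishes to transfer care of their TPN and CVC permanently to another institution". The catheter in question will normally be the home PN catheter, and the definition does cover it. A reader might infer that the endpoint is aimed at the wrong catheter. The documents do not support that: the rule is too wide, and it does not exclude the target.

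A reader might also infer that other-line infections do enter the endpoint and dilute it materially. The documents do not support that either. No section mentions a second central line or how often one occurs, so the effect could be small, as the 1-point row shows. Nor is the whole fall in power attributable to the wording. When other-line events are carved out of the planned 30%, most of the loss reflects a smaller home-catheter effect, which no redefinition restores.

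The definition is introduced as the CDC's. Whether that source carries its own attribution rules cannot be checked from these documents; none is printed.

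These points limit the size of the finding. They leave the literal reading standing: as printed, an infection of a line placed after home PN ended is a primary event, and an endpoint definition should not depend on readers inferring otherwise.

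**Conclusion.** The concern holds as a weakness of definition. The rule has no link to the home PN catheter, so infections of other central lines can count and can pull the arms together. The direction is clear; the size is not known.

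Under the assumed 30% versus 10% with 45 per arm, restricting the endpoint gains about 2 power points if other lines supply 1 of the 30 control points, and about 5 to 12 if they supply 3 to 8. Under a halving the gain is about 1 to 6. The effect sizes, 1:1 allocation and other-line shares are all assumptions.

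The gains are upper illustrations. An infection during a readmission in which the home catheter stays in alongside a temporary line would still count, so restriction mainly removes events after the home catheter is out. Nor does the restriction require the catheter to be the source: a bloodstream infection from another site with the home PN catheter in place would still meet the definition. The change is worth making because it is cheap and brings the endpoint closer to what the video targets, not because a large loss of power has been shown.

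**What to change.** 1. In the Methodology definition, replace the unspecified central venous catheter with the catheter used for home PN, or its replacement for home PN. A replacement home catheter is still handled by the patient and belongs in the endpoint.
2. At the Visit 4 record review, add one field stating which catheter or catheters were in place at each positive culture. Conceal the arm from the existing abstractor where feasible, because the documents describe no blinding of this review and the field calls for judgement.
3. State that events with both the home PN catheter and another line in place count.
4. List events in other central lines only separately, outside the primary count, and add them back in a sensitivity analysis.

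The cost is one changed phrase, a short rule for concurrent lines and one abstraction field, from records already being reviewed. The downsides are slightly fewer counted events and some judgement in chart abstraction. The change should be made before events are abstracted.

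### Enrolling 100 with 10% loss leaves 90 patients, below the 93 the plan says it needs, and the 70% power is tied to no stated video-arm rate

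*Combined protocol and SAP*

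**What the plan says.** The sample size is justified in one paragraph, under Statistical justification in the combined protocol and SAP. Its inputs are "With 30% rate of bloodstream infection, and a 70% power and 95% confidence interval". From these it concludes that "the total sample size required would be 93 patients in order to see a reduction in the rate of bloodstream infection". The allowance for attrition follows: "Suppose a 10% rate for loss to follow-up, the total subjects will be 100 patients". The section on the number of experimental subjects repeats the result: "One hundred (100) subjects will be included in the study".

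The comparison being sized is the primary one, in which "the rate of CRBSI will be calculated and compared between the TPN video group and the control group" by an unpaired Student's t test.

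No infection rate for the video arm, size of reduction, sidedness, allocation ratio or formula appears in this paragraph or elsewhere. The Background describes an education trial in another population in which "the 42 patients had 50% less CRBSI in a five-month period", but the calculation does not refer to it.

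**The concern.** There are two separate faults in the paragraph.

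- **Attrition.** The plan names a required number, a loss rate and an enrolment figure, and the three are inconsistent. After the loss it expects, it will not have the number it says it needs.
- **Target effect.** A two-group sample size depends on both event rates. Only one is given, so the 93 cannot be checked and the 70% power has no effect attached to it.

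This paragraph is the only support for the size of the primary comparison. A reader cannot tell from it that the trial is adequately sized, even at a modest 70%, only for a very large reduction. If the result is not significant, there is no declared effect to judge it against.

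**Working it through.** **Inputs from the plan (Statistical justification).** Reference rate 30%, taken as the control arm because the text does not say; power 70%; 95% level; required total 93; loss 10%; enrolment 100.

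**Assumptions, because the plan is silent.** 1:1 allocation, two-sided 5%, equal loss in both arms.

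**Step 1: attrition, from the plan's figures alone.**

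- Expected evaluable: 100 × 0.90 = 90, which is 93 − 90 = 3 short.
- Enrolment needed: 93 / 0.90 = 103.3, so 104. Check: 103 × 0.90 = 92.7 and 104 × 0.90 = 93.6.
- Adding 10% instead: 93 × 1.10 = 102.3, so 103.
- Loss that 100 can absorb: 1 − 93/100 = 7%.

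Neither convention gives 100.

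**Step 2: can 93 be reproduced?** Not from the stated inputs, because the second rate is missing. With the unpooled formula, n per arm = (1.960 + 0.524)² × [p₁(1 − p₁) + p₂(1 − p₂)] / (p₁ − p₂)²:

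- 30% vs 10%: 46.29 per arm, 92.6 in total. The pooled formula gives 48.72 per arm, 97.4 in total.
- 30% vs 15%: 92.58 per arm.

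So 93 fits a total for a reduction from 30% to 10%, and it also happens to fit a per-arm number for a halving. The text says total. Solving 2n = 93 for the video-arm rate gives 10.0% (unpooled) or 9.6% (pooled). A one-sided 5% test would put it at 12.1% or 11.8%, roughly a 60% reduction.

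The required total depends heavily on the missing rate (pooled formula, 70% power, each arm rounded up):

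| Assumed video-arm rate | Total required |
|---|---|
| 5% | 56 |
| 10% | 98 |
| 15% | 192 |
| 20% | 462 |

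**Step 3: power actually available.** The exact column is the planned two-sided pooled-variance t test applied to 0/1 outcomes, by enumeration of the two binomial distributions.

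| Comparison | Evaluable | Unpooled | Pooled | Exact t test |
|---|---|---|---|---|
| 30% vs 10% | 93 | 70.2% | 67.9% | 68.4% (control 47, video 46) or 69.3% (46, 47) |
| 30% vs 10% | 90 | 68.8% | 66.5% | 68.5% |
| 30% vs 15% | 90 | 41.0% | 39.7% | 39.8% |

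Enrolling 104 would leave about 94 evaluable, for which the exact power for 30% vs 10% is 70.5% (47 per arm). With 90 evaluable, the video-arm rate detectable at 70% power is 9.8% (unpooled), 9.3% (pooled) or 9.7% (exact).

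The 15% row only illustrates a halving; the plan does not adopt that target.

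**The case against.** The strongest reply is that the attrition error hardly matters. For the planned t test at 30% vs 10%, going from 93 to 90 patients changes exact power by between +0.1 and −0.9 points, depending on which arm has the extra patient at 93. The 1.5-point loss appears only in the normal approximations. This is right: on its own, the shortfall is close to a rounding matter. It remains an inconsistency between figures the plan itself states, and the rounding went below the stated requirement.

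A second reply is that 90 evaluable may be pessimistic. The outcome is read from the medical record at one year, the care team telephones weekly, and outside records are obtained as part of usual care, so an infection before loss might still be counted. That is possible. But permanent transfer of care ends participation, the plan does not say how such patients are analysed, and the 10% loss is its own assumption.

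Third, the two-thirds figure rests on 1:1 allocation and a two-sided test, neither of which is stated. This stands as a caveat. The 95% level makes two-sided the natural reading, and the one-sided alternative still implies a reduction of about 60%.

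Fourth, a confidence interval for the difference would show which effects a null result excludes. That is true and useful, but it does not supply the target that the stated power needs.

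**Conclusion.** The concern holds on both counts and should be fixed. The attrition inconsistency follows from the plan's own numbers and needs no assumption: 100 enrolled with 10% loss gives 90, against 93 required, and 104 would be needed. Its effect on power is small.

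The absence of a video-arm rate carries more weight. Under 1:1 allocation and two-sided 5%, the trial has about 70% power only for a fall from 30% to roughly 10%, and about 40% for a fall to 15%. The 93 is not shown to be wrong. The match with 30% vs 10% is an inference and should not be read as the sponsor's stated assumption.

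**What to change.** 1. State the control and video-arm rates, sidedness, allocation ratio and formula that produced 93, and confirm that 93 is a total. This comes first, because an attrition correction to 104 would be the wrong repair if 93 were a per-arm number.
2. Then either keep 100 and restate the power for 90 evaluable patients, or raise enrolment to 104.

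Possible wording, if the target was 30% vs 10% and enrolment stays at 100:

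> A total of 100 patients will be enrolled, allocated 1:1. With 10% loss, 90 evaluable patients give about 66–69% power (exact t test 68.5%) to detect 30% versus 10% at two-sided 5%, and about 40% power for 30% versus 15%.

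Keeping 100 costs only wording and a slightly less favourable stated power. The alternative costs four more patients. Neither changes an endpoint, an analysis or a study procedure.
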